Figure 4. RBC microparticle counts before (left) and after (right) washing with the CATS.

[figure not shown]
[figure not shown]
[figure not shown]

Figure 4. Lung injury biomarkers in patients who do and do not develop ARDS.

PHASE I/II CLINICAL TRIAL EVALUATING POINT-OF-CARE RBC WASHING TO PREVENT RBC-ASSOCIATED RESPIRATORY COMPLICATIONS FOLLOWING CARDIAC SURGERY

Study population: Study procedures are summarized in Figure 5. We will enroll a total 154 patients receiving at least one RBC transfusion on the operative day. We anticipate this will require randomizing up to **190 patients** in this trial (95 per group). Adult patients (age ≥ 18) who are planned to undergo cardiac surgery at one of the two participating institutions and who have a predicted RBC transfusion requirement of ≥ 4 units will be screened for the exclusion criteria outlined in Table 4. Predicted RBC transfusion requirements will be determined utilizing a recently published large-volume blood transfusion (LVBT) prediction model (>4 units of RBC).⁷³ A cut off of 4 predicted units of RBC administration was chosen because: 1) this transfusion volume has been associated with increased risk of pulmonary complications following cardiac surgery⁵⁸; 2) we have previously identified this transfusion volume as a common “dose” in patients who experience TRALI and/or TACO^{28, 39,42}; and 3) this threshold would still identify a sizable cardiac surgery population, ensuring study feasibility.

Study procedures:

Screening: Study coordinators will screen all adult (age ≥ 18) patients who are scheduled to undergo coronary artery bypass graft surgery with or without valve repair/replacement, complex cardiac valve surgery, pericardial resection, and/or ascending aortic surgery in one of the two participating institutions. Eligible patients with a predicted transfusion requirement of 4 or more units will be approached before their elective surgical procedure by a study coordinator for consent. After confirming the patient's inclusion and exclusion criteria, the study coordinator at the respective institution will obtain informed consent and assign a study ID number to the study participant. Screening logs will be maintained at each site to allow generation of a CONSORT diagram.

Table 4. Exclusion criteria.

Exclusion Criteria	Justification
• Emergency surgery	Inability to randomize/perform study procedures
• IgA deficiency	Not ethical to randomize to standard issue RBCs

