• History of severe recurrent transfusion reaction	Not ethical to randomize to standard issue RBCs
• Refusal to receive allogeneic RBCs	Inability to administer intervention of interest
• Refusal to provide informed consent	Not ethical to enroll into trial
• Prevalent Acute lung injury prior to randomization	Inability to adequately assess outcome
• Prevalent hydrostatic pulmonary edema prior to randomization	Inability to adequately assess outcome
• Expected hospital stay < 48 hours	Incomplete study procedures and outcome data
• Not anticipated to survive > 48 hours	Incomplete study procedures and outcome data
• Previously enrolled in this trial	Violation of the independence assumption
• No intention to measure cardiac output parameters during surgical procedure	Inability to assess key physiologic parameters outlined in the study protocol
• Use of home oxygen therapy	Inability to assess oxygen use outcome
• Complex RBC antibody profiles	Washing not feasible due to testing delays
• Need for the use of irradiated RBCs	Intervention contraindicated
• Intention to place a cardiac mechanical assist device	Inability to assess key physiologic parameters outlined in the study protocol

Randomization: Randomization will occur at the time of consent and analyses will be conducted using a modified intention-to-treat principle (See statistical considerations below). Randomization to RBC washing or control group (standard-issue RBC) will be conducted by the study's electronic data management system's Balance (Medidata) algorithm. This software uses dynamic minimization stratified by clinical center. The software will return a confirmation of the randomization indicating the study participant's treatment allocation status. A note will be placed into the EHR identifying the patient as a study participant and the transfusion medicine service will have unblinded, electronic access to the treatment assignment. Randomization and screening will halt after the 154th study participant has undergone surgery and received at least one RBC transfusion on the operative day. Patients randomized but awaiting surgery will continue study participation.

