assessments (total Hb, CFH, haptoglobin) will be analyzed locally at the enrolling sites using standard clinical assays. **Aim 1c:** A 6-ml sample will be taken pre- and post-wash from the already anticoagulated intervention RBC units. **Aim 2:** 10 mls of blood will be drawn from each study participant at baseline, following the first RBC unit administered, at 6 hours after the end of first study RBC transfusion, and 18 hours after the end of first study RBC transfusion. All samples will be centrifuged, alloquotted and frozen. Samples will be batch shipped to Mayo Clinic Rochester and analyzed in [name] laboratory at Blood Systems Research Institute (BSRI), and a separate aliquot provided for [name] laboratory (neutral lipids only).

Biomarkers: Thawed platelet poor plasma will be diluted with assay buffers and measured (**aims 1c/2c**: sCD40L, CCL5/RANTES; **aims 2a/2c**: IL-6, IL-8, PAI-1; Plasma will be used to perform ELISA-based measurements of RAGE (**aim 2a/2c**). NT-proBNP (**aim 2c**) will be measured. **RBC-derived microparticles (aims 1c/2c):** Thawed platelet-poor plasma will be spun, then labeled in preparation for flow cytometric measurement. Vesicles will be lysed with NP-40 detergent and samples re-run to confirm results and allow setting of gates. **Free hemoglobin (aims 1c/2c): will be measured.** **Neutral lipids (aims 1c/2c):** Following the addition of ice-cold methanol, proteins will be precipitated, and non-polar lipids will be extracted/analyzed using high-pressure liquid chromatography (LC) interfaced into the electrospray source of a triple quadrupole mass spectrometer (MS) (liquid chromatography coupled to electrospray ionization mass spectrometry [LC/MS/MS]). Lipid concentrations will be estimated using ratios to an internal standard ($^2\text{H}^8$ -5-HETE), as previously described.^{101,103}

Predictor variables other than the intervention: Pertinent baseline demographics and clinical characteristics such as age, sex, race, and comorbidities will be recorded. Additional predictor variables will include: vital signs and laboratory values that are obtained during the course of routine care, APACHE IV score, administration of statins, ace-inhibitors, insulin, amiodarone, or steroids; blood product administration for the up to day 28 or hospital discharge, whichever comes first, daily fluid status, and vasopressor requirements.

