Statistical Considerations (prepared in collaboration with our statistical: Aim 1 is centered on the clinical and technical feasibility of on-demand RBC washing (hypothesis 1a). Feasibility is defined as the administration of protocol RBCs instead of "off-protocol" standard-issue RBCs. Simon's two-stage design will be used to determine if the protocol needs to be modified to prepare RBCs prior to the surgical procedure. The null hypothesis rate for feasibility is $p \leq 0.75$ versus the alternative that $p \geq 0.90$, where p is the probability of successfully preparing and administering the intervention RBCs. Stage 1 of the design will examine the first 16 cases randomized to RBC washing. If 12 or fewer transfusions were deemed "feasible", the protocol will be modified to pre-wash RBCs (see limitations). If 13 or more are feasible, an additional 32 cases will be evaluated. Should 39 or fewer (of the 48 studied) not be feasible, the protocol will be modified to pre-wash. If 40 or more cases meet the feasibility definition, the remainder of the study will go as originally planned. (Sample size/ design calculations details: PASS 2008, alpha=0.10, beta=0.10, Optimal design). The safety endpoint for aim 1 is the change in hemoglobin level (hypothesis 1b). The change in hemoglobin after the first transfused unit will be used as the primary safety measure. Wilcoxon rank sum tests will be used to compare change in hemoglobin levels between randomized groups. The change in concentrations of soluble BRMs (e.g.

neutral lipids; hypothesis 1c) will be assessed using paired t-tests. There is > 80% power to detect a 0.4 SD difference pre- to post-washing with 78 washed RBC products. Should there be fewer (due to feasibility), power will decrease. However, the magnitude of differences observed in preliminary data (92% reduction, Figure 4) is many times larger than an effect size of 0.4. Therefore, power for this hypothesis should not be a concern.

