Aim 2 examines the changes in biomarkers levels measured over three time points (Baseline, no later than 30 minutes after the end of the first RBC transfusion, 6 hours (+ / - 30 minutes) from the end of first study RBC transfusion, and 18 hours (+ / - 30 minutes) from the end of first study RBC transfusion. Mixed models will be fit to model the linear trajectory of these biomarkers. A model with a random slope and intercept will be considered initially, and the primary parameter of interest will be the treatment group by time interaction. For this analysis, a “modified” intention to treat (ITT) principle will be considered. Only patients randomized to RBC washing who receive at least one unit of the washed cells will be included from RBC washing group in the analysis. Those not receiving RBC washed cells will be in the considered the control group. The reason for this is this aim is focused on mechanistic action and demonstrating biologic plausibility prior to formal evaluation of clinical outcomes (which would be analyzed using traditional ITT considerations). Since the functional form of the changes in biomarkers over time is not known, a discrete (2 D.F. test) representation of time will also be used to gauge the linearity assumption as well as provide a sensitivity analysis to the primary regression model. Standard mixed modeling practices will be utilized (e.g., assessment of residuals, verification of variance components, nested modeling to simply variance components and covariance patterns, etc). This modeling scenario will be conducted for each biomarker of interest. Since prior research have noted that these outcomes are “clustered”, the methodology by Shi et al. will be used to adjust for multiple comparisons.¹⁰⁴ We will also compute O’Brien’s nonparametric global test statistic to provide an overall measure of treatment effect between the two treatment groups.

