The effects of storage duration will also be assessed. The mean age of the transfused blood products will be determined. This value will be used to test for effect modification (interaction with treatment). Specifically, the main effect of RBC age, its interaction action with treatment, time and the treatment-by-time interaction term will be used to determine if the biomarker trajectories are affected by RBC age. It is hypothesized that the washing protocol will attenuate the effects of age resulting in more uniform trajectories over the range of RBC age where as the unwashed RBC will show increases in biomarker values as RBC age increases.

Sample Size Considerations: The sample size for this clinical trial is based on the mechanistic outcomes detailed for Specific Aim 2a. Table 2 in Fremont et al. was used to provide estimates of the range of effect sizes for the biomarkers considered in this study.⁸⁰ Using an approximation of the standard deviation from the interquartile range ($SD \approx IRQ/1.35$), the median effect size was found to be 0.4. This magnitude of change would be relevant, and appropriate to power this study on. With equal allocation between the groups, the sample size for this study is estimated to be $n=78/group$ ($\alpha=0.10$, two-sided; see additional statistical considerations below). Actual power is expected to be higher on account of the repeated measures design. To allow for drop out and “non-feasible” cases, we plan to enroll and randomize patients until 154 patients have undergone surgery and had at least one transfusion on the operative day. We anticipate this may require randomizing up to 190 total patients. Any patients randomized and awaiting surgery when the 154th patient is achieved will also be included. The final sample size may be adjusted further based on the feasibility findings observed in the two-stage design.

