Aim 3 will utilize standard analytical measures for comparing randomized treatment groups with ITT. For data that may be skewed (e.g., length of ventilation, ICU stay), Wilcoxon rank sum tests will be used to compare groups. Serial measurements (oxygen saturation) will be analyzed using longitudinal summary statistics (e.g., AUC, mean value). It should be noted that the intermediate clinical outcomes are not being powered for in this study. Estimates of precision (confidence intervals) along with range of responses will be used to guide subsequent trial designs (e.g. a larger phase II/III trial with clinical outcomes as the primary outcome of interest).

Additional statistical considerations: Consistent with early phase clinical trials, we have selected a level of significance higher than the traditional 0.05. This will facilitate advancement of the technique should it prove feasible and demonstrates potential efficacy. It is noted that multiple testing may increase the overall family wise error rate, so further research, particularly with clinical events, will be needed to quantify clinical efficacy of the approach. Missing data is expected to be minimal during the course of the study given the close surveillance the surgical and ICU environment provides. Missing specimens may occur in the event of patient discharge, death or administrative issues. Initial analyses will be conducted under the assumption of MCAR/MAR (ignorable missing). Sensitivity analyses using multiple imputation and pattern mixture models will be used to assess the robustness of the model assumptions. The analysis of specific aim 2 proposes to use a modification of the ITT principle. Justification for this is that it is a mechanistic aim with blinded examiners. We are interested in quantifying the effects of washing as clearly (and perhaps ideally) this is an early phase trial. In Aim 3, the clinical outcomes will be assessed using the traditional ITT definition to provide a more realistic measure of the effect size for planning subsequent studies.

Protocol Addendum:

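### Randomisation is stratified by centre but no between-arm analysis accounts for centre, so the Aim 1b and Aim 3 Wilcoxon tests are conservative if centre predicts outcome, and the Aim 2 tests may err in either direction

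*Combined protocol and SAP*

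**What the plan says.** The trial recruits adults "who are planned to undergo cardiac surgery at one of the two participating institutions". On allocation, the Randomization section states: "This software uses dynamic minimization stratified by clinical center".

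The analyses are set out under Statistical Considerations:

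- **Aim 1a:** a Simon two-stage rule, applied to cases in the washing arm only.
- **Aim 1b:** "Wilcoxon rank sum tests will be used to compare change in hemoglobin levels between randomized groups".
- **Aim 1c:** paired t-tests, pre-wash against post-wash.
- **Aim 2:** "A model with a random slope and intercept will be considered initially", with the treatment-by-time interaction as the parameter of interest. A discrete-time version, interactions with RBC age and O'Brien's global test are added. Washing-arm patients who receive no washed cells are counted as controls.
- **Aim 3:** for skewed outcomes such as ventilation time and ICU stay, "Wilcoxon rank sum tests will be used to compare groups".

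Centre is not named in any of these, nor in the list of predictor variables other than the intervention. Specimen Handling and Laboratory Assays says the Aim 1b safety measurements "will be analyzed locally at the enrolling sites using standard clinical assays".

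**The concern.** When allocation is balanced within a factor that predicts the outcome, the true variance of the treatment difference no longer contains the between-centre part. An analysis that ignores the factor still estimates its standard error from the total variance. The standard error is then too large, the test rejects less often than its nominal level, and power is given up.

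Some centre differences are plausible here. Hemoglobin, cell-free hemoglobin and haptoglobin are measured at each site. Transfusion decisions are left to the clinical service, and each centre has adopted its own awakening and breathing-trial protocols, which bear on ventilation time, the main Aim 3 outcome.

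The direction matters most for Aim 1b. Its hypothesis is that the rise in hemoglobin is comparable, but it is examined with a test for difference, so a conservative test makes a real difference easier to miss. Aim 3 is meant to inform later trials through its confidence intervals, which would be wider than they need be if they too ignore centre.

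**Working it through.** **1. Reproduce the plan's own figure.** Sample Size Considerations gives two-sided alpha 0.10, equal allocation and 78 per group, and says "the median effect size was found to be 0.4". Power for Aim 2a is not stated; 80% is assumed. Then n = 2 × [(1.645 + 0.842)/0.4]² = 77.3, rounded up to 78 per group, which matches. At the target of 154 patients (77 per group) the noncentrality is 0.4 × √(77/2) = 2.482 and power is Φ(2.482 − 1.645) = 79.9%.

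**2. Translate a centre gap into a variance share.** For two equal centres differing by g within-centre SDs, R² = (g²/4)/(1 + g²/4). This gives 0.0625/1.0625 = 5.9% at g = 0.5, 0.25/1.25 = 20% at g = 1, and 0.5625/1.5625 = 36% at g = 1.5.

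**3. Type I error when centre is ignored** (as-randomised arms, balanced within centre): 2[1 − Φ(1.645/√(1 − R²))].

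| Gap (SD) | R² | 1.645/√(1 − R²) | Formula | Simulated, unstratified Wilcoxon | Simulated, van Elteren |
|---|---|---|---|---|---|
| 0 | 0% | 1.645 | 0.100 | 0.097 | 0.096 |
| 0.5 | 5.9% | 1.696 | 0.090 | 0.085 to 0.090 | 0.094 to 0.097 |
| 1 | 20% | 1.839 | 0.066 | 0.067 to 0.068 | 0.099 to 0.103 |
| 1.5 | 36% | 2.056 | 0.040 | 0.036 to 0.041 | 0.104 |

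The ranges come from separate simulation runs with 154 patients.

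**4. Power forgone, with the 0.4 effect expressed in total SDs.** Unadjusted power is Φ((2.482 − 1.645)/√(1 − R²)); adjusted power is Φ(2.482/√(1 − R²) − 1.645).

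| R² | Unadjusted | Adjusted | Forgone (points) |
|---|---|---|---|
| 0% | 79.9% | 79.9% | 0 |
| 2% | 80.1% | 80.6% | 0.5 |
| 5% | 80.5% | 81.6% | 1.2 |
| 10% | 81.1% | 83.4% | 2.3 |
| 20% | 82.5% | 87.1% | 4.6 |

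**5. Same check, with the 0.4 effect expressed in within-centre SDs.** Unadjusted power is Φ(2.482 − 1.645/√(1 − R²)) and adjusted power stays at 79.9%. At R² 10% and 20% the unadjusted values are 77.3% and 74.0%, so 2.6 and 5.9 points are forgone. Simulated Wilcoxon power at a 1 SD gap is 71% unstratified against 77 to 78% stratified. At 1.5 SD it is about 62% against 77%. With no centre gap, the unstratified and stratified tests agree to within simulation error (77.3% against 77.6% in one run, 78.4% against 78.1% in another).

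**6. Aim 2, treatment-by-time.** Per-patient slopes over four time points stood in for the mixed model (8,000 runs per setting). With a centre gap in level only, type I error was 0.099 to 0.106, because the gap drops out of within-patient slopes. With centre explaining 20% of slope variance it was 0.064 to 0.069.

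**7. Aim 2, reclassification.** A single-measure outcome was simulated with 39 washing-arm patients at one centre, some of whom were moved to control (20,000 runs). Type I error without adjustment:

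| Moved at that centre | R² 5% | R² 10% | R² 20% |
|---|---|---|---|
| 0 | 0.092 | 0.083 | 0.067 |
| 4 | 0.096 | 0.089 | 0.074 |
| 10 | 0.109 | 0.122 | 0.142 |
| 16 | 0.141 | 0.187 | 0.273 |

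With a centre term it stayed between 0.098 and 0.106. For the treatment-by-time test, R² here should be read as the centre's share of slope variance.

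**The case against.** The strongest reply is that this is an efficiency point with no demonstrated effect. No centre effect is reported, and gaps of 1 and 1.5 SD would mean that centre explains 20% and 36% of outcome variance, which nothing in the documents supports. The Aim 1b test is on change in hemoglobin, so a constant assay offset between sites cancels. The Aim 2 assays are run by the collaborating laboratories, not site by site. The weaning protocols are described as a means of standardising care, and the text does not say that they differ between centres. Aim 3 is exploratory and expressly not powered.

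Most of this stands and limits the size of the point. It does not remove it: differences in assay scale, transfusion practice or weaning would not cancel, and stratifying costs nothing material if they are absent.

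A reader might go further and infer any of the following, which the documents do not support:

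- **That every planned test has p-values that are too large.** The Simon rule and the paired t-tests are not between-arm comparisons. The Aim 2 interaction test is untouched by a centre gap in level. After reclassification its p-values could be too small instead.
- **That planned power falls to about 71% or 62%.** Those figures need a 1 or 1.5 SD gap and an effect scaled to within-centre SD. Scaled to total SD, unadjusted power stays at or above about 80%. The 0.4 is also an Aim 2a biomarker figure; Aims 1b and 3 state no effect size.
- **That stratifying would support the claim of comparability in Aim 1b.** A non-significant difference test, stratified or not, is not evidence of comparability.

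**Conclusion.** The point holds in a limited form. The plan stratifies allocation by centre and leaves centre out of every between-arm analysis.

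For the Aim 1b and Aim 3 Wilcoxon tests the consequence, if centre predicts outcome, is conservatism: slight when centre explains a few percent of variance, and a loss of roughly 5 to 6 points of power at 20%.

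For Aim 2, on whose outcomes the trial is sized, the test is conservative only if centres differ in biomarker trajectory. The direction becomes uncertain if reclassified patients cluster at one centre: moving 4 of 39 left the test conservative, while moving 10 or more pushed it above 0.10.

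These sizes assume 80% planned power, 77 per group, near-exact balance within centre and normally distributed outcomes with a centre shift. The centre effects, and the numbers moved in the reclassification check, are assumed and not taken from the documents. Centre splits of 50:50 and 70:30 gave similar results.

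**What to change.** - **Aims 1b and 3:** replace the Wilcoxon rank sum test with the centre-stratified (van Elteren) version.
- **Aim 2:** add centre and centre-by-time as fixed effects in every mixed model, including the discrete-time sensitivity version. A centre main effect alone would leave the treatment-by-time test essentially unchanged.
- If centre is to be left out of any between-arm analysis, state the reason in the SAP.

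The Aim 1a and Aim 1c analyses need no change. The cost is SAP wording and two extra terms in the Aim 2 models. Centre is already held because allocation uses it, and simulation showed no material loss of power when centres do not differ.
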